7.1.1 Hypothesis Testing

All inferential hypothesis tests will be two-sided at $\alpha = 0.05$ significance level. There will be no adjustment of Type I error for multiple comparisons due to exploratory nature of this early phase study.

7.1.2 Defining the Study Baseline

The baseline value for each variable is defined as the last value recorded on or before the first administration of randomized study medication.

7.1.3 Handling of Multiple Observations

For laboratory data, a subject may have multiple scheduled or unscheduled laboratory values for the same analyte that are associated with a protocol defined visit. To define the baseline, all scheduled or unscheduled lab values prior to the first dose of randomized study medication will be sorted by collection time and last sample collected in chronological order will be taken as the baseline.

For multiple post-baseline values associated with the same scheduled visit, mean values will be computed first and will be used as the value associated with that visit. However, when summarizing the laboratory parameter shift tables, the worst value of the multiple observations will be used when applicable.

All results, scheduled or unscheduled, will be listed.

7.1.4 Handling Missing Data or Outliers

In general, no imputation of missing data will be done except for those described below:

Values below the lower limit of quantification of an assay (<LLOQ) will be assigned LLOQ/2 for the purposes of analysis.

Missing or partial start/stop dates for AEs will be imputed with the following algorithms:

For AE start date, the imputation rule is to conservatively capture as many treatmentemergent AE (TEAE) as possible:

- If "day" is the only missing field, impute the "day" as the later one between the first day of the month and the first dose date if their "month" are the same.
- If "day" and "month" are the only missing fields, impute the "day" and "month" as the later one between January 1 of the year and the first dose date if their "year" are the same.
- If "day", "month", and "year" are all missing, to be conservative, the AE will be assumed to occur on the same day as the first dose was administered.

For AE stop dates, imputation is needed to calculate the duration of the event observed during the study period. Note that on AE listings, the duration will be printed with the ">" symbol to indicate the actual duration is longer than the number presented. The algorithms are:

- If "day" is the only missing field, impute the "day" as the former one between the last of the month and the last study visit date if their "month" are the same.
- If "day" and "month" are both missing, impute it as the former one between December 31 of the year and the last study visit date if their "year" are the same.
- If "day", "month", and "year" are all missing, the AE will be assumed to stop on the same day as the last study visit date.

Outliers will not be excluded from analysis.

[figure not shown]

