9.2 Adverse Events

An AE is any untoward medical occurrence in a subject administered a pharmaceutical product, without regard to the possibility of a causal relationship with this treatment. Lack of drug effect is not an AE in clinical trials because the purpose of the clinical trial is to establish drug effect.

Any documented pregnancy will be tracked and followed through outcome. While pregnancy itself is not considered an AE or an SAE, any pregnancy complications or elective termination of a pregnancy for medical reasons will be recorded as an AE and evaluated as a possible SAE.

Prior to enrollment, study site personnel will note the occurrence and nature of each subject's medical condition(s) in the appropriate section of the source document and eCRF. During the study, site personnel will again note any change in the pre-existing condition(s) and the occurrence and nature of any AEs.

CANDIN will be administered in accordance with the US labeled indication for assessment of the subject's DTH response to Candida antigen. AE collection will begin at the time of the DTH injection (Screening Visit 1).

CANDIN administered intralesionally is the investigational product in this study. Treatment-Emergent AEs (TEAEs) will be those arising after the first intralesional wart(s) injection.

If a subject experiences an AE after the informed consent document is signed, but before CANDIN is Nielsen- CFW-2D Page 38 of 54

Protocol Final version 5.0: 06Dec2016

administered for assessment of the DTH response, the event will be recorded as a non-treatment emergent AE in the source document. If the subject is randomized, the non-treatment emergent event will also be captured in the eCRF. If the subject screen fails, the event will not be captured in the eCRF or in the clinical database.

AEs reported as related to CANDIN administered for assessment of the DTH response will be described in the source document and assessed for expectedness and regulatory reportability using the Candin package insert. If the subject is randomized, the AE related to Candin for the DTH assessment will also be captured in the eCRF.

Injection site AEs may be captured from either subject diaries or during Treatment and Follow-up Visits. In all cases, causality and severity of injection site TEAEs are assessed by Investigator as described in Sections 9.2.1 and 9.2.2, respectively.

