7.3.1 Adverse Events

TEAEs are defined as those occurring during or after the first wart injection of randomized study medication, or existing prior to the time of and worsening after the time of the first study dose, through final Follow-up Visit (V15) or Early Termination/Withdrawal. AEs with onset date prior to the first administration of randomized study medication will be classified as pretreatment AEs.

All AEs are to be coded with Medical Dictionary for Regulatory Activities (MedDRATM) version 17.0.

The frequency (event counts) and incidence (number and percent of subjects) of TEAEs, serious TEAEs, TEAEs leading to withdrawal, TEAEs by severity (most severe grading from

the same preferred terms within the same subjects), and TEAEs by causality (Related versus Not Related), frequent TEAEs (incidence \geq 5% in any treatment groups) will be summarized.

Injection site TEAEs, defined by any preferred terms containing the phrase of "injection site", will be summarized further.

DTH-related AEs that occurred during the DTH Screening time period (e.g., prior to the receiving the randomized study medication) will be summarized separately for DTH Safety population.

All further details collected for AEs will be presented in a listing.

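### The AE start-date imputation in SAP 7.1.4 ignores a recorded stop date, so an AE that ended before the first wart injection can be counted as treatment-emergent

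*SAP*

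**What the plan says.** SAP 7.1.4 has three rules for an incomplete AE start date.

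- Day missing: "impute the 'day' as the later one between the first day of the month and the first dose date if their 'month' are the same".
- Day and month missing: take the "later one between January 1 of the year and the first dose date if their 'year' are the same".
- Everything missing: "to be conservative, the AE will be assumed to occur on the same day as the first dose was administered".

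The stated aim is that "the imputation rule is to conservatively capture as many" TEAEs as possible. Stop dates have a separate algorithm with a different purpose: "For AE stop dates, imputation is needed to calculate the duration of the event observed during the study period". Neither part refers to the other.

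SAP 7.3.1 then sorts events on the resulting date: "AEs with onset date prior to the first administration of randomized study medication will be classified as pretreatment AEs". An AE with onset at or after the first wart injection is a TEAE, and so is an earlier one that worsens after it.

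Under Protocol 9.2, AE collection opens with the DTH injection at Screening Visit 1, and AEs of randomized subjects go into the eCRF. The flow chart in Protocol Appendix A places that visit between day -30 and day -2.

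**The concern.** A conservative date rule settles doubt in favour of calling an event treatment-emergent. If the stop date is recorded and lies before the first wart injection, no such doubt exists. The event cannot have begun at or after dosing, and it cannot have worsened afterwards, so it meets neither part of the TEAE definition. The three rules can still place its onset on the first-dose date, which is later than its own end.

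TEAE incidence is named as the primary safety endpoint in Protocol 14.5.2 and SAP 7.3. What is at stake is whether those tables contain events that the trial's own records show to be over before treatment. Because the design collects AEs for up to about a month before dosing, such events are foreseeable.

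**Working it through.** The plan states no figure on this point, so there is nothing to reproduce. The check applies the rules literally.

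**Inputs.** The three start-date rules (SAP 7.1.4); classification by onset (SAP 7.3.1); first screening visit on day -30 to -2 (Protocol Appendix A); 39 subjects per CANDIN arm (Protocol 6.1, SAP 3.1). **Assumptions.** Calendar year 2017. Where the known month or year differs from that of first dose, SAP 7.1.4 gives no explicit value; the first of that month, or 1 January, is used.

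**Step 1: one record.** First wart injection 24 March 2017; recorded AE stop 10 March 2017.

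| Recorded start | Imputed start | As written | With a stop-date check |
|---|---|---|---|
| March 2017 | later of 1 and 24 March = 24 March | TEAE | pretreatment |
| 2017 | later of 1 January and 24 March = 24 March | TEAE | pretreatment |
| nothing | 24 March | TEAE | pretreatment |

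The imputed onset is 14 days after the recorded end. If duration were computed from it, stop - start + 1 would be -13 days. By contrast, a stop on or after 24 March would leave real doubt, and the TEAE label would then be the intended result.

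**Step 2: when the rules bite.** Take every first-dose date in the year with every onset from day -30 to day -2, each event ending before first dose: 365 × 29 = 10,585 combinations.

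- *Day missing.* The rule misclassifies only if onset and first dose share a calendar month. A month of L days contributes (L - 1)(L - 2)/2 such combinations: 435 for L = 31, 406 for L = 30, 351 for L = 28. The total is 7 × 435 + 4 × 406 + 351 = 5,020, and 5,020/10,585 = 47%. Otherwise the imputed date is the first of the earlier month, and the event correctly stays pretreatment.
- *Day and month missing.* 464 combinations cross into the previous year, so 10,585 - 464 = 10,121 are misclassified (96%).
- *All missing.* 10,585 (100%).
- *With a stop-date check.* 0 of 10,585 in each pattern.

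**Step 3: sensitivity of the day-missing share.** This was simulated with 200,000 AEs per scenario, screening gap uniform on 2 to 30 days, and exponential durations with means of 2, 4 and 7 days. Among events over before dosing, the share is 66.5%, 63.6% and 61.0% if onset is uniform within the gap. It is 47.3%, 44.9% and 42.2% if onset is 0 to 2 days after the first screening visit. The range is therefore about 42% to 67%, depending on assumed onset timing.

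All these shares are conditional on a record having both an incomplete start date and a known pre-dose stop. They do not predict trial counts.

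**Step 4: effect on incidence.** One affected subject with no other TEAE adds 1/39 = 2.6 percentage points to a CANDIN arm. A subject who has another TEAE adds nothing at subject level. If a share q of each arm falsely gains a TEAE, independently of true TEAEs, incidence p becomes p + (1 - p)q and a difference between arms is multiplied by (1 - q). With q = 1/39 in every arm and an assumed true difference of 30 points, the result is 30 × 38/39 = 29.2 points.

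**The case against.** The strongest reply is that the trigger is rare. A record must lack part of its start date and also carry a known stop before dosing, all within about 30 days. Protocol 7.12 provides 30 minutes of observation after the DTH injection and a diary for delayed reactions. The flow chart has that diary reviewed at Visit 2 and AEs reviewed at Visits 1, 2 and 3. Month and year will nearly always be recoverable, so the fully missing case is close to empty and its 100% should carry little weight. All of this stands, and it is why the number is likely to be small.

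A second reply is that pre-dose DTH-related AEs have their own summary in the DTH Safety population (SAP 5.1 and 7.3.1). That shows the intended handling. It does not formally stop the date rule from acting on those events, and it does not cover other screening AEs.

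A third reply is that the rule is openly conservative and errs only upward. The direction is right: no safety signal is hidden. But that aim addresses uncertain onset, and a recorded pre-dose stop removes the uncertainty that matters.

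**Conclusion.** The point holds as a minor defect in the rule. As written, SAP 7.1.4 and 7.3.1 together can class an AE as treatment-emergent when its own recorded stop date shows that it ended before the first wart injection. Nothing in the available text overrides this. The number of affected records is not given and is probably small; any error is an over-count.

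A reader might infer three stronger things that the documents do not support.

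- *That the rule materially dilutes the CANDIN-placebo comparison.* Even one false case per 39 subjects in every arm barely moves a difference, and the available text plans counts and percentages for TEAEs, with no between-arm test.
- *That the AE listings will show negative durations.* SAP 7.1.4 ties the start-date rule to TEAE capture and mentions duration only for stop dates. Negative values follow only if the imputed start is used to compute duration.
- *That 42% to 67% of screening AEs will be misclassified.* Those are shares of an unknown, possibly empty, set of records and rest on assumed onset timing.

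**What to change.** Add one condition ahead of the three start-date rules in SAP 7.1.4:

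> If the recorded AE stop date (complete, or partial but decisive) is before the first dose of randomized study medication, the AE is classified as pretreatment and its start date is not imputed to the first-dose date; it is imputed as the earliest date compatible with the known start fields, or left missing if none are known. No imputed start date may be later than the recorded stop date.

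Keep the conservative rules for all other records. In the same edit, it would help to state the value used when the known month or year differs from that of first dose.

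The cost is a short SAP addition and a small change to the date-derivation code. The downside is a slightly lower TEAE count, limited to events shown to have ended before treatment.

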7.2 Efficacy Analyses

7.2.1 Analyses of Primary Endpoint

If the area of a measured wart at baseline becomes 0 at a post-baseline evaluation visit, the wart will be considered as completely resolved. For each of the four treatment groups, the number and percent of subjects achieving complete resolution of the primary injected wart(s) will be calculated and summarized.

[figure not shown]

7.2.4 Interim Analyses

There are no formal interim analyses planned for this study; however, there will be a medical assessment of the safety data including review of data from subject diaries from the first eight subjects in Cohort 2 after the last of these subjects receives his/her third injection, before allowing inclusion in Cohort 3. Refer to the definition of cohorts in Section 3.1 for further details. There will also be a medical assessment of the safety data, including subject diaries (See Section 7.3.4) from the first five subjects of Cohorts 2 and 3 after the first injection, before allowing inclusion of more than one subject per day; or else a limited inclusion rate will continue.

7.2.5 Pooling of Sites

Study centers/sites will be pooled according to the following rules:

- Two highest enrolling sites will not be pooled.
- All other sites will be pooled together to create a single pooled site.

Site effect on the primary efficacy endpoint will be descriptively explored by summarizing the primary efficacy endpoint separately for the two highest enrolling sites and pooled site.

7.3 Safety Analyses

The analysis of safety data will be performed for the Safety population unless otherwise stated. The primary safety endpoint is the incidence of TEAEs as defined as any new AEs or existing AEs that have worsened during or following the first wart(s) injection with Candin (Visit 3) through the final Follow-up Visit (V15), or Early Termination/Withdrawal. Other safety endpoints include clinical laboratory evaluations, vital signs, and changes in skin examinations as well as general physical examinations.

7.3.1 Adverse Events

TEAEs are defined as those occurring during or after the first wart injection of randomized study medication, or existing prior to the time of and worsening after the time of the first study dose, through final Follow-up Visit (V15) or Early Termination/Withdrawal. AEs with onset date prior to the first administration of randomized study medication will be classified as pretreatment AEs.

All AEs are to be coded with Medical Dictionary for Regulatory Activities (MedDRATM) version 17.0.

The frequency (event counts) and incidence (number and percent of subjects) of TEAEs, serious TEAEs, TEAEs leading to withdrawal, TEAEs by severity (most severe grading from

the same preferred terms within the same subjects), and TEAEs by causality (Related versus Not Related), frequent TEAEs (incidence \geq 5% in any treatment groups) will be summarized.

Injection site TEAEs, defined by any preferred terms containing the phrase of "injection site", will be summarized further.

DTH-related AEs that occurred during the DTH Screening time period (e.g., prior to the receiving the randomized study medication) will be summarized separately for DTH Safety population.

All further details collected for AEs will be presented in a listing.

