3.2 Secondary Endpoints

1. Incidence of site injection AE for all subjects and TEAE for subjects randomized to CANDIN

Protocol Final version 5.0: 06Dec2016

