14.5.2.1 Analysis of Adverse Events

TEAEs (those arising after the first intralesional wart injection in this study) will be summarized by treatment, SOC, and preferred term defined by MedDRA. The number of events and number of events by severity, the number of subjects, and the percent of subjects who experienced at least one TEAE will be presented for each SOC and for each preferred term by treatment group. TEAEs that lead to early withdrawals and serious TEAEs will be summarized in the same manner. Additional details will be provided in the SAP. Injection site TEAEs will be analysed separately from other TEAEs.

DTH-related AEs will be analysed separately by Sponsor and Medical Monitor to determine FDA reportability.

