- 2. If the medical Investigator deems appropriate because of tolerance issues the injection schema may be changed to every 3 weeks instead of 2 weeks for a maximum of 10 doses.
- 3. Female of childbearing potential only. Serum pregnancy at screening and urine pregnancy test at other visits.
- 4. At selected sites, for a maximum of 10 subjects per cohort.
- 5. Post 48h of DTH injection from V1.
- 6. Cohort 1 only.
- 7. DTH Diary
- 8. Applicable only if there is complete resolution of the primary injected wart(s).
- 9. One for Cohort 1 and 2; and up to 4 in Cohort 3.
- 10. If complete resolution of all common warts, not just the primary injected wart(s), is observed at any of the visits following Baseline, the procedures described under Visit 13 will be performed. This visit also will be performed in the event of an early termination.
- 11. To be initially assessed at Visit 3 and prior to the first injection in case of selection and mapping of non-primary common wart(s) for injection (V4 to V12). To be re-assessed at the site of resolved primary and non-primary injected wart(s) must be recorded as an AE if at Baseline (V3), or prior to the first injection in case of selection and mapping of non-primary common wart(s) for injection (V4 to V12) it was assessed as absent.
- 12. Prior to injection.
- 13. On certain occasions, administering the DTH challenge at V1 may result in a difficulty scheduling V2 at the 48 hour time required (for example V1 on a Thursday or Friday resulting in V2 on a weekend). The investigator may perform the DTH challenge on an additional visit after V1 (subvisit) in order to schedule an acceptable V2, provided the DTH challenge is performed within 1 week of V1 and a urine pregnancy test is performed if required for a given subject. Urine pregnancy testing not required for women of non-childbearing potential defined as post-menopausal for at least 2 years or surgically sterile (tubal ligation, oophorectomy, or hysterectomy).
- 14. V1 and V13 should not be scheduled on a weekend if at all possible due to shipping restrictions of blood samples.

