4.2 Secondary Endpoints

Secondary endpoints include the following:

1. Assessment of safety and tolerability of Candin:

Incidences of DTH Challenge immediate reactions and immediate injection hypersensitivity/reactions after study treatment, and all other treatment-emergent adverse events.

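### The SAP picks out injection-site TEAEs by words in the coded term, so scarring and hypopigmentation at injected warts can be left out of the injection-site summary

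*SAP*

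**What the plan says.** **How the events are selected.** SAP 7.3.1 defines injection-site TEAEs as those "defined by any preferred terms containing the phrase of" *injection site*, and plans a further summary of them. Coding is in MedDRA 17.0. The available text shows no location flag, term list or coding convention to support the text search.

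**Which local events the plan creates.** Table 1 in SAP 3.2 schedules hypopigmentation and scarring assessments from V3 to V15. Its footnote 11 reads, in part, "To be re-assessed at the site of resolved primary and non-primary injected wart(s) must be recorded as an AE", on condition that the change was absent at baseline or before the first injection of a non-primary wart. As printed, the sentence seems to have lost some words.

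**What the summary feeds.**
- Protocol 3.2 states the secondary endpoint in two parts: "Incidence of site injection AE for all subjects and TEAE for subjects randomized to CANDIN".
- Protocol 14.5.2.1 adds that "Injection site TEAEs will be analysed separately from other TEAEs" and gives no text rule.
- SAP 4.2 words the endpoint differently: DTH challenge reactions, immediate injection reactions, "and all other treatment-emergent adverse events".

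**How sites classify these events.** Protocol 9.2 says "Injection site AEs may be captured from either subject diaries or during Treatment and Follow-up Visits", with causality and severity judged by the investigator. Protocol 9.2.2 sets one severity scale for events at the injection site and another for all other events.

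**The concern.** The endpoint asks where an event happened, but the SAP asks how its coded term is worded. Usually the two agree. They can part for residual skin change at a treated wart. If a site writes *injection site scar*, the event can be found. If it writes *scar at wart*, the coded term may lack the phrase. Both describe the same event in the same place.

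At stake is a descriptive summary of local tolerability, not a hypothesis test. It still matters, because under Protocol 3.2 the injection-site part is the only part of the secondary endpoint that covers both randomized treatments, so it carries the comparison with placebo. The loss also need not be even. If re-assessment takes place where a wart has resolved, a treatment that resolves more warts exposes more of its subjects to an AE that the text search can miss.

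**Working it through.** The documents give no incidence for injection-site events, scarring or hypopigmentation, so there is no figure of the plan to reproduce. The check is how many subjects could be affected, and in which group.

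**Inputs from the documents**
- Group sizes (Protocol 6.1, SAP 3.1): 39 CANDIN and 13 placebo per cohort. Check: 156 × 3/4 = 117 = 3 × 39, and 156/4 = 39 = 3 × 13.
- Resolution rates (Protocol synopsis, Sample Size Determination): 24% for pooled placebo and 70% for one active arm. The other two active arms have no stated rate.

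**Assumed inputs**
- *q*, the chance of new scarring or hypopigmentation given resolution: 5% to 20%.
- *m*, the share of those events coded without the phrase: 25% to 100%.
- *s*, the share of affected subjects who already have another TEAE carrying the phrase: 0 for an upper limit.
- All three are taken as equal across groups.

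**Step 1. Subjects with a resolved primary wart** = n × resolution rate.
- Arm at 70%: 39 × 0.70 = 27.3.
- Pooled placebo: 39 × 0.24 = 9.4.
- Ratio of rates: 0.70/0.24 = 2.9.

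Across all CANDIN subjects the answer depends on the two unstated arms:

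| CANDIN arms | CANDIN (of 117) | Placebo (of 39) | CANDIN share of count | Ratio of rates |
|---|---|---|---|---|
| all at 70% | 81.9 | 9.4 | 90% | 2.9 |
| one at 70%, two at 24% | 46.0 | 9.4 | 83% | 1.6 |
| all at 24% | 28.1 | 9.4 | 75% | 1.0 |

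The last row reflects the 3:1 allocation alone. A CANDIN majority by count is therefore not evidence of a difference in rate.

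**Step 2. Undercount of subjects, in percentage points** = 100 × resolution rate × *q* × *m* × (1 − *s*).

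With *s* = 0:
- Lowest corner: 70 × 0.05 × 0.25 = 0.9 points in the 70% arm; 24 × 0.05 × 0.25 = 0.3 on placebo.
- Middle: 70 × 0.10 × 0.50 = 3.5 points; 24 × 0.10 × 0.50 = 1.2.
- Highest corner: 70 × 0.20 × 1 = 14.0 points; 24 × 0.20 × 1 = 4.8.

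In subjects, the highest corner is 27.3 × 0.20 = 5.5 of 39 in that arm and 9.4 × 0.20 = 1.9 of 39 on placebo.

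Over all 117 CANDIN subjects at the middle values, the undercount is 81.9 × 0.05 = 4.1 subjects (3.5 points) if every arm is at 70%, and 46.0 × 0.05 = 2.3 subjects (2.0 points) if only one is.

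**Step 3. Overlap.** Incidence counts each subject once. With *s* = 50% in both groups, the highest corner halves to 7.0 and 2.4 points. Event counts and counts by preferred term are not reduced by this overlap with other injection-site terms.

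**Limit of the count.** Step 1 uses primary warts only. Footnote 11 also covers non-primary injected warts, and Cohort 3 injects two to four warts per visit, so more sites, and in Cohort 3 possibly more subjects, could be re-assessed.

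**The case against.** A reader might infer that these events drop out of the secondary endpoint. The documents do not support that. SAP 4.2 takes in all other TEAEs, so the event counts there whatever its term. Protocol 3.2 also counts TEAEs in CANDIN subjects, so a CANDIN event missed by the text search stays in the protocol endpoint through its second part; only a placebo event could leave it altogether. Missed events also remain in the overall TEAE tables by system organ class, preferred term, severity and causality, and in the listings.

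A reader might likewise infer a bias in favour of CANDIN across the safety results, or a loss of 7 to 14 points in each CANDIN group. Neither follows. The direction concerns the injection-site summary only and needs CANDIN to resolve more warts than placebo. The 70% is assumed for one arm. The points come from assumed *q* and *m*, and subjects with another injection-site TEAE are already counted.

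Three further objections carry some weight:
- Footnote 11 is garbled, and Table 1 schedules the assessment at every visit from V3. Re-assessment at resolved sites is the natural reading, but not a certain one.
- SAP 7.3 names changes in skin examinations as a safety endpoint, and parts of both documents are withheld, so a separate scarring summary or a coding convention may exist. A separate summary would not correct the visible definition of injection-site TEAEs; a convention requiring the phrase could make the text search adequate.
- The grading table in Protocol 9.2.2 covers pain, tenderness, redness and swelling, not scarring. It says how to grade those reactions; it does not limit which AEs count as being at the injection site.

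**Conclusion.** The point holds for the injection-site TEAE summary. As written, the SAP rule can leave out local AEs that the plan itself requires to be recorded, and so can understate the injection-site component of the protocol's secondary endpoint. It does not remove them from safety reporting as a whole.

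The size cannot be known from the documents. The ranges above, 0.9 to 14.0 points in an arm at 70% and 0.3 to 4.8 points on placebo, are upper limits for the assumed *q* and *m*. The larger CANDIN undercount rests on three conditions: CANDIN resolves more warts, footnote 11 means re-assessment at resolved sites, and *q*, *m* and *s* are similar between groups. With equal resolution and those same inputs, the rates are affected equally. No test and no sample-size figure depends on this. It is a modest defect in a descriptive comparison, and worth correcting because the correction is cheap.

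**What to change.** In SAP 7.3.1, define an injection-site TEAE as any TEAE located at an injected wart site. Identify these events by blinded medical review of the verbatim terms, or from an eCRF location item if one already exists, and complete this before database lock. State that the hypopigmentation and scarring events of footnote 11 are included. Keep the text search as a cross-check and list the events on which the two methods disagree. Repair the wording of footnote 11 at the same time.

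The cost is a short change to the SAP and one blinded pass through the AE listing. The sponsor should expect that the reported rate of local AEs may rise.
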